7.2.1 Blood Samples

Blood samples will be collected by qualified and trained site personnel. Participants should be in a seated or supine position during blood collection.

The maximal total volume of blood drawn for each participant will be around 12.5 mL for safety analysis. Samples will be sent to an external laboratory for testing.

Hematology
Mean corpuscular volume (MCV)
Mean corpuscular hemoglobin concentration (MCHC)
Hematocrit
Red blood cell (RBC) count
Differential WBC count
Platelet count
Hemoglobin
Mean corpuscular hemoglobin (MCH)
White blood cell (WBC) count

Clinical Chemistry		
Sodium		Potassium

Chloride	Carbon Dioxide
Blood Urea Nitrogen	Creatinine
Glucose	Total Protein
Albumin	Total Bilirubin
Alkaline Phosphatase	Alanine aminotransferase (ALT)
Estimated Glomerular Filtration Rate	Aspartate aminotransferase (AST)
Calcium	

Table 1 - Clinical Chemistry & Hematology Assessments

7.2.2 Serum Pregnancy Test

Serum pregnancy test will only be performed during the screening visit for all female participants

Serum Pregnancy Test
Qualitative human chorionic gonadotropin (HCG) test

Table 2 – Serum Pregnancy Test

7.2.3 Urine Samples

Urine samples will be collected for the urine drug screen (at screening session), urine pregnancy test (at all sessions except screening), and safety urinalysis (at screening session). The urine drug screen and pregnancy tests will be performed by study personnel at the study site. The urine sample collected for urinalysis will be sent to an external laboratory for testing.

In case of any positive pregnancy test, the Investigator or designee will inform the participant about the risks associated with smoking during pregnancy.

	Urinalysis
рН	
Red blood cell traces	
Bilirubin	
Protein	
Glucose	
Specific gravity	
Nitrite	
WBC Esterase	

Table 3 - Urinalysis Assessments

Drug Screening
Amphetamine
Cocaine
THC
Methamphetamine
Opiates

Table 4 - Drug Screening

7.2.4 Urine Pregnancy Test

The urine pregnancy tests will be performed by study personnel at RRC. Urine pregnancy tests will be performed for all females at all visits except screening.

7.2.5 Expired Air CO Breath Test

Carbon Monoxide (CO) in participant's exhaled breath (expressed as ppm) will be measured using a Vitalograph CO Monitor. Participants must have an expired air CO reading at V1 of at least 10 ppm for inclusion into this study. This test will be repeated at each of the laboratory sessions.

7.2.6 Medical History and Concomitant Disease

Relevant medical history and concomitant disease will be documented at the screening visit (V1). Medical history is defined as any condition that started and ended prior to V1. A concomitant disease is defined as any condition that started prior to V1 and is still ongoing at V1 (this may also include findings detected during the screening visit).

7.2.7 Prior and Concomitant Medication

All medication taken four weeks prior to the screening visit (V1) and during the study will be documented using a source document. Medications which are stopped before V1 will be considered as prior medication. Medication which was started prior to V1 and which is still being taken by the participant during the study as well as medication that is initiated after V1 will be considered as a concomitant medication. This applies to both prescription and over-the-counter products (e.g., vitamins).

Records of prior and concomitant medications taken include the drug name (preferably both generic and trade name), route of administration, dose/unit, frequency of use, indication, the start and if applicable, the stop date. Any therapy changes (including changes of regimen) during the study will be documented.

The questionnaires will be administered to the participants using paper questionnaires and/or an electronic data collection system. The timing of these questionnaires is outlined in the Schedule of Events 8.5.

7.2.8 Demographics

Sex, date of birth, race and ethnicity will be recorded for each participant according to Section 8.5.

7.2.9 Height and Weight

Height and weight will be measured and recorded according to Section 8.5.

7.2.10 Physical Examination

A physical examination will be performed according to Section 8.5. The physical examination will include review of general appearance, hair and skin, head, eyes, ears, nose and throat, neck, chest, abdomen, dentition, cardiovascular, musculoskeletal and neurological systems. The physical examination is to be conducted by a designated fully trained and licensed medical staff.

Appropriate medical advice will be provided to the participant if any medical findings requiring health care are identified.

7.2.11 AE/SAE Reporting

AEs/SAEs will be assessed using questionnaires and face-to-face interviews at the indicated time points and spontaneous reporting from the time of ICF signature until the EOS for the participant (see Section 8.5).

7.2.12 Electrocardiogram (ECG)

ECG recording will be performed as per RRC Standard Operating Procedures at screening. A standard 12-lead ECG will be recorded after the participant has rested for at least 5 minutes in a supine position.

The following parameters will be documented: heart rate, PR interval, QRS interval, QT interval, and QTc interval (Bazett). Every ECG will be assessed as normal, abnormal – not clinically significant, or abnormal – clinically significant.

ECG printouts will be interpreted by a qualified physician or physician assistant. Any printouts of ECGs on thermo-sensitive paper will be photocopied and stapled together for inclusion in the source documents and signed by the qualified physician or physician assistant.

7.2.13 Vital Signs

Vital signs (systolic and diastolic blood pressure, pulse rate and respiratory rate), will be measured in sitting position after the participant has rested for at least 5 minutes according to Section 8.5. At the screening visit, blood pressure and heart rate will be measured again at least two minutes later in a standing position.

7.2.14 Questionnaires

The questionnaires will be administered to the participants using paper questionnaires and/or an electronic data collection system. The questionnaires will be asked according to Section 8.5.

7.2.14.1 *10-Item Perceived Stress Scale (PSS-10)*

Self-report questionnaires are the simplest method for obtaining a rapid evaluation of a participant's realized stress levels. The Perceived Stress Scale (PSS) was developed in 1983 as a psychometrically valid measure of perceived stress. A 2011 study reviewed the use of the PSS in a sample of participants who smoked, evaluating three different versions; the PSS-14 (14-item questionnaire), the PSS-10 (10-item questionnaire), and the PSS-4 (4-item questionnaire). The results from this 2011 study confirmed the psychometric properties of all three versions. Our study will utilize the PSS-10 during all visits after enrollment (V2 through V7) to evaluate self-reported perceived stress levels.

7.2.14.2 *6-Item State-Trait Inventory (STAI)*

In 2011, [name] from University of California, San Francisco, published a review of available validated methods for accurately measuring anxiety. Her review focused on self-reported measures of general anxiety. She reviewed three different models; the State-Trait Anxiety Index, the Beck Anxiety Inventory, and the anxiety subscale of the Hospital Anxiety and Depression Scale. The STAI demonstrated excellent reliability and good validity, and is both responsive and sensitive to change. The STAI is among the most widely used measures of general anxiety. Our study will utilize the 6-item STAI during all visits after enrollment (V2 through V7) to evaluate self-reported anxiety levels.

7.2.14.3 PHQ-9 -- The Patient Health Questionnaire

The Patient Health Questionnaire PHQ-9 for Depression will be used to screen for current (within 2 weeks) depression. Potential participants who score >9 (or who score >0 on item #9 ("Thoughts that you would be better off dead, or of hurting yourself in some way")) will be excluded from study participation, and, at the discretion of the study physician/physician assistants, referred to appropriate psychiatric treatment. Participants will respond to this questionnaire at all visits. This questionnaire will be administered at every visit, including the screening visit (V1 through V7).

7.2.14.4 Modified Cigarette Evaluation Questionnaire (mCEQ)

The mCEQ assesses the degree to which participants experience the reinforcing effects of smoking. This questionnaire will be administered after enrollment and prior to commencing the investigational products (V2 and V3).

7.2.14.5 MNWS – Minnesota Nicotine Withdrawal Scale

The MNWS will be used at all visits after "quit day" (V4 through V7) to assess nicotine withdrawal symptoms including craving and mood effects. Participants will be asked to assess the following seven symptoms (on a 5-point scale ranging from 0 to 4, where 0 = none, 1 = slight, 2 = mild, 3 = moderate, 4 = severe):

- Desire or craving to smoke
- Anger, irritability, frustration
- Anxiety or nervousness
- Difficulty of concentrating
- Impatience, restlessness
- Hunger
- Depression

7.2.14.6 FTND -- The Fagerström Test for Nicotine Dependence

The Fagerström Test for Nicotine Dependence is a six-item questionnaire developed by Karl-Olov Fagerström and is used to determine someone's level of nicotine dependence. The scores obtained on the test allow the classification of nicotine dependence in three different levels: mild (0-3 points), moderate (4-6 points), and severe (7 -10 points). This questionnaire will be given at all visits (V1 through V7).

7.2.14.7 WI-PREPARE – Wisconsin Predicting Patients' Relapse Questionnaire

The WI-PREPARE is a seven-item questionnaire that is designed to assess a participant's susceptibility to smoking relapse. The questionnaire includes measures of physical dependency, environmental factors and smoking characteristics. Participants will respond to this questionnaire after enrollment and prior to the selected "quit day" (V2 and V3).

7.2.14.8 Prior and Concomitant Medication

At each visit, participants will report any changes in medication use, including the use of supplements, vitamins, over-the-counter medications, and prescription medications.

7.2.14.9 Smoking History Questionnaire

The Smoking History is a questionnaire designed to help assess the participant's current and past smoking habits. This questionnaire will be administered at screening (V1) and will include questions about the number of years participants have smoked combustible cigarettes (CC), the number of CCs per day smoked over the last 12 months, brand of CCs, use of other tobacco products and use of nicotine replacement therapy or other smoking cessation treatments. This questionnaire will also be used to check eligibility criteria.

7.2.14.10 Registration Form

This form is an internal questionnaire designed to collect demographic information about participants. It will be administered at screening (V1).

7.2.14.11 Medical History Form

The Medical History form is an internal questionnaire designed to help assess the participant's current health and any health history. This questionnaire also includes questions about all medications (include prescription medications, other-the-counter medications or supplements) taken in the past 30 days. It is designed to help assess the participant's current health and health history and is used to help determine eligibility. This form is administered at the initial screening visit (V1).

7.2.14.12 Review of Systems

The Review of Systems is an internal questionnaire administered at screening (V1) to help assess the participant's current health and health history by asking about the presence of a list of symptoms.

7.2.14.13 *Employment History*

The Employment History is an internal questionnaire designed to collect information about a participants' social economic status. Participants will be presented this questionnaire after enrollment, at the second visit (V2).

7.2.14.14 *Adverse Effects*

During each visit after enrollment (V2 through V7), participants will respond to adverse events based on a mild/moderate/severe rating. The questionnaire will use both targeted questions and open-ended questions to access for any adverse effects/events. Participants will respond to SMS text message inquiries for study specific adverse effects, on a daily basis, commencing after enrollment (see Section 8.8).

7.2.14.15 *Medication Compliance*

Participants will be queried via SMS text messages whether they have been compliant with taking the study specific medications. These messages will commence after the second visit and continue through the End of Study (see Section 8.8).

7.2.14.16 *Smoking Status*

SMS text messages will be sent to participants starting after enrollment, through the End of Study, to ascertain the participants smoking status (see Section 8.8).

8 Sessions

8.1 SCREENING SESSION (V1)

Eligibility of participants to participate in this study will be assessed at the screening visit (V1). The ICF will be signed, dated and timed prior to any other screening procedures (see Section 8.5).

The sequence of the following assessments will be at the discretion of the Investigator (or designee) after signature of the ICF.

- Questionnaires
 - Smoking History
 - Registration Form
 - Medical History (with Review of Systems)
 - Patient Health Questionnaire (PHQ-9)
- Prior and Concomitant Medication
- Expired air CO breath test
- Urine collection for urinalysis and drug screen
- Vital signs (blood pressure, heart rate, respiratory rate)
- Height and weight / BMI
- Temperature
- Electrocardiogram (ECG)
- Physical examination

- Blood collection for safety laboratory testing (including pregnancy test for females)
- Instructions on use of the SMS messaging/questionnaire system

8.2 5-DAY OBSERVATION PERIOD

After verification of eligibility (approximately two days after screening), participants will be enrolled in the study and commence a five-day observational period. Participants will be called and given instructions on the use of the SMS system which will administer questions about adverse effects and smoking status in order to collect baseline data prior to start of the study drugs.

8.3 Pre-Quit Session (V2)

After completion of a minimum five-day observational period, participants will come to the Center for assessment, training (including brief quit smoking counseling), and dispensing of study drugs. The quit date will be scheduled for the day after Visit 3, and seven days after commencing the study drugs. The sequence of the following assessments will be at the discretion of the Investigator or designee.

- Document concomitant disease and medication changes
- Physical examination (if indicated)
- Expired air CO breath test
- Vital signs (blood pressure, heart rate, respiratory rate)
- Weight
- Brief smoking cessation counseling (QuitAssist Counseling Handout)
- Urine pregnancy test (all females)
- Dispensing of study drugs
- Verification of proper use of the SMS messaging (refresher training, if needed)
- Questionnaires
 - Employment History
 - o FTND
 - PSS-10
 - o 6-Item STAI
 - Adverse Effects Questionnaire
 - Patient Health Questionnaire (PHQ-9)
 - Wisconsin-Predicting Patient's Relapse (WI-PREPARE)
 - Modified Cigarette Evaluation Questionnaire (mCEQ)
 - Smoking Status (daily via SMS survey, commence after visit)
 - o Medication Compliance (daily via SMS survey, commence after visit)

8.4 Day before quit date (V3)

Six days after starting medications (one day prior to quit date), participants will return to the Center for assessment and collection/dispensing of study drugs. The sequence of the following assessments will be at the discretion of the Investigator or designee.

- Document concomitant disease and medication changes
- Physical examination (if indicated)

- Expired air CO breath test
- Vital signs (blood pressure, heart rate, respiratory rate)
- Weight
- Brief review of smoking cessation counseling (if indicated)
- Urine pregnancy test (all females)
- Collection and dispensing of study drugs
- Assess medication compliance
- Verification of proper use of the SMS messaging (refresher training, if needed)
- Questionnaires
 - o FTND
 - o PSS-10
 - o 6-Item STAI
 - Adverse Effects Questionnaire
 - Patient Health Questionnaire (PHQ-9)
 - Wisconsin-Predicting Patient's Relapse (WI-PREPARE)
 - Modified Cigarette Evaluation Questionnaire (mCEQ)
 - o Smoking Status (review with participant and continue daily via SMS survey)
 - Medication Compliance (review with participant and continue daily via SMS survey)

8.5 Post-Quit Sessions (V4-V7)

Sessions scheduled after the quit-smoking date will be conducted at 2 weeks after the quit date and then at 4-week intervals until the end of the 12-week treatment period. The sequence of the following assessments will be at the discretion of the Investigator or designee.

- Document concomitant disease and medication changes
- Physical examination (if indicated)
- Expired air CO breath test
- Vital signs (blood pressure, heart rate, respiratory rate)
- Weight
- Brief review of smoking cessation counseling (if indicated)
- Urine pregnancy test (all females)
- Collection and dispensing of study drugs (collection only at the EOS visit)
- Assess medication compliance
- Verification of proper use of the SMS messaging (refresher training, if needed)
- Questionnaires
 - o FTND
 - o PSS-10
 - MNWS
 - o 6-Item STAI
 - o Adverse Effects Questionnaire
 - Patient Health Questionnaire (PHQ-9)
 - Smoking Status (review with participant and continue daily via SMS survey until End of Study)
 - Medication Compliance (review with participant and continue daily via SMS survey until End of Study)

8.6 6-Month Follow Up

Participants who successfully complete the study and are abstinent at the final visit (V7), will be contacted six months after the quit day utilizing an automated SMS messaging system, to ascertain their current smoking status.

8.7 SCHEDULE OF EVENTS

Visit Assessments and Procedures		Screening Session	5-day observation period	Laboratory Sessions						6-month f/u
		V1		V2	V3	V4	V5	V6	V7	
Informed Consent and Guidance		•								
Inclusion/Exclusion Criteria		•								
Enrollment			•*							
Prior and Concomitant Medication		•		•	•	•	•	•	•	
Questionnaires	Smoking History Questionnaire	•								
	Registration Form	•								
	Employment History			•						
	Medical History/Review of Systems	•								
	10-item Perceived Stress Scale (PSS-10)			•	•	•	•	•	•	
	6-Item State-Trait Inventory			•	•	•	•	•	•	
	Wisconsin-Predicting Patient's Relapse (WI-PREPARE)			•	•					
	Modified Cigarette Evaluation Questionnaire (mCEQ)			•	•					
	The Fagerström Test for Nicotine Dependence (FTND)			•	•	•	•	•	•	
	Patient Health Questionnaire (PHQ-9)	•		•	•	•	•	•	•	
	Minnesota Nicotine Withdrawal Scale (MNWS)					•	•	•	•	
	Smoking Status (via daily SMS text)		•	•	•	•	•	•	•	•
	Medication Compliance (via daily SMS text)			•	•	•	•	•	•	
	Adverse Effects Questionnaire (at visits and daily SMS Text)		•	•	•	•	•	•	•	
	Safety Laboratories	•								
Serum Pregnancy Test (Females)		•								
Urine Pregnancy Test (Females)				•	•	•	•	•	•	
Urine Drug Screen		•								
CO Breath Test		•		•	•	•	•	•	•	
	ECG	•								
Vitals	Blood Pressure	•		•	•	•	•	•	•	
	Heart rate	•		•	•	•	•	•	•	
	Temperature	•								
	Respiratory rate	•		•	•	•	•	•	•	
	Weight	•		•	•	•	•	•	•	
Height		•								
BMI		•								
Physical Examination		•		•#	•#	•#	•#	•#	•#	
Collect Used/Unused Blister Packs					•	•	•	•	•	
Dispense Study Drugs in Blister Packs				•	•	•	•	•		

^{*}After evaluation of safety labs, prior to start of observational period

[#] Targeted examination as needed

8.8 SMS Messaging

- 8.8.1 Daily SMS Message (after enrollment, prior to V2) Participants will receive a text with a link to a survey to access the following:
 - How soon after you wake up did you smoke your first cigarette?
 - 1-Within 5 Minutes, 2-6 to 30 Minutes, 3-31 to 60 Minutes, 4-After 60 Minutes
 - How many cigarettes did you smoke today?
 - What was your level of stress today?
 - 1-No Stress, 2-Mild Stress, 3-Moderate Stress, 4-A Lot of Stress, 5-Extreme Stress
 - · How well did you sleep last night?
 - 1-No problems, 2-Mild problems, 3-Moderate problems, 4-A Lot of problems, 5-Extreme problems
 - Did you feel nauseated today?
 1-No nausea, 2-Mild nausea, 3-Moderate nausea, 4-A lot of nausea, 5-Extreme nausea
- 8.8.2 Daily SMS Message (after Visit 2) -- Participants will receive a text with a link to a survey to assess the following:
 - Have you smoked any cigarettes today?
 - If yes, how soon after you wake up did you smoke your first cigarette?
 1-Within 5 Minutes, 2-6 to 30 Minutes, 3-31 to 60 Minutes, 4-After 60 Minutes
 - O How many cigarettes did you smoke today?
 - Did you take your study drugs this morning?
 - Did you take your study drugs this evening?
 - What was your level of stress today?
 - 1-No Stress, 2-Mild Stress, 3-Moderate Stress, 4-A Lot of Stress, 5-Extreme Stress
 - How well did you sleep last night?
 - 1-No problems, 2-Mild problems, 3-Moderate problems, 4-A Lot of problems, 5-Extreme problems
 - Did you feel nauseated today?
 - 1-No nausea, 2-Mild nausea, 3-Moderate nausea, 4-A lot of nausea, 5-Extreme nausea
- 8.8.3 6-Month follow up SMS Message -- Participants will receive a text with a link to a survey to assess the following:
 - Have you smoked a cigarette since your last visit?
 - o If yes, are you still smoking cigarettes right now?

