2 STUDY OBJECTIVES AND ENDPOINTS

2.1 EFFICACY OF VARENICLINE AND HYDROXYZINE FOR STRESS AND SLEEP

A maximum of fifty (50) smokers will receive the FDA-approved dosing for both varenicline and hydroxyzine. These medications have been approved by the FDA for use by healthy, non-pregnant adults at the doses and frequencies specified in this study.

Participants enrolled in the study will take the FDA approved starter kit of varenicline for the first week of medication administration (0.5 mg nightly for days 1-3, then 0.5 mg twice daily for days 4-7). During the first week, participants will also receive hydroxyzine dosed in a similar manner, 50 mg nightly for the first 3 days, then twice daily, 25 mg in the morning and 50 mg at night. After the first week, participants will receive the FDA-approved dose of varenicline (1 mg twice daily) combined with hydroxyzine, 25 mg in the morning and 50 mg at nighttime. All medications will be dosed orally. The FDA has approved the 50 mg dose of hydroxyzine for treatment of nausea, anxiety, and insomnia. The morning dose of hydroxyzine is limited to 25 mg to minimize the sedative effects of this antihistamine, while the evening dose is prescribed at 50 mg to maximize the antiemetic, anxiolytic, and sedative properties. Dose adjustments for hydroxyzine by licensed medical providers may occur based on adverse effects reported by participants (e.g. daytime sedation...stop the AM dose of hydroxyzine, difficulty waking in the am...decrease nighttime dose of hydroxyzine). Participants will be contacted with a follow-up call by Research Medical Staff within 72 hours of any dose adjustment. Trial medications will continue until the participant returns for the End-of-Study visit, approximately 12 weeks after initiation of the medications.

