3.1.4 Stepwise Evaluation Algorithm

3.2 STUDY PLAN

After obtaining informed consent, adult smokers will be enrolled into the study. There will be an observational period of at least five days to obtain baseline data on use of combustible cigarettes and stress/anxiety and nausea symptoms.

Varenicline Dose = 0.5 mg QPM x 3 days, then 0.5 mg BID x 4 days, then 1.0 mg BID x 11 weeks Hydroxyzine Dose = 50 mg QPM x 3 days, then 25 mg QAM + 50 mg QPM

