4.8.3 SMS Response Window

The SMS response window will be open until the next SMS message is sent.

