13.1.2 Side Effects / Tolerability

The hypothesis that hydroxyzine reduces the incidence of nausea, one of the most common side effects of varenicline, will be evaluated by comparison to the benchmark of 30% (20% above placebo rate of 10%) observed in clinical trials of varenicline.³⁶ Initially, 25 participants will be recruited and then the possibility of recruiting 25 more (total N=50) depending on an interim analysis, as follows:

- If 0-3 participants out of 25 (12% or less) report nausea, we would conclude the treatment is highly promising at the interim stage and go directly to an RCT (Branch 1).
- If 4-6 participants (out of 25) report the side effect, then the treatment will be deemed sufficiently promising to recruit an additional 25 participants (Branch 2). If 10 or less of the total 50 report the side effect of nausea (20% or less), a follow-up RCT would be warranted; otherwise the treatment would be deemed unpromising.
- If 7 or more out of 25 (28% or more) report the side effect of nausea in the interim analysis, then we would conclude it is futile to continue the pilot and the study would be terminated (Branch 3).

The frequency of treatment-emergent side effects (i.e., those that begin or worsen after the initiation of treatment) will be tabulated. Due to the problem of Type II error posed by significance testing numerous side effect outcomes (especially if corrections are imposed for multiple comparisons), descriptive statistical methods will instead be used, supplemented by calculation of confidence intervals and p-values as a flagging device to highlight differences worthy of further attention.³⁷ Hypothesis testing will be conducted for only two outcomes: 1) proportion of participants that withdraw from the study due to side effects; 2) overall adherence (i.e., proportion of scheduled doses taken) assessed by daily medication diaries and returned capsules.

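### The daily dose questions have no send time, dose date or 'not yet' answer, so diary adherence can be biased, most plausibly downward

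*Combined protocol and SAP*

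**What the plan says.** Section 8.8.2 sets one daily survey after Visit 2. It has one item on the morning dose and one on the later dose: "Did you take your study drugs this evening". Appendix 14 shows the form, where both items take Yes or No only. Neither place gives a send time or a date for the dose. On late replies, Section 4.8.3 says: "The SMS response window will be open until the next SMS message is sent".

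The schedule in Section 3.2 is PM only for three days and twice daily after that: "Varenicline Dose = 0.5 mg QPM x 3 days, then 0.5 mg BID x 4 days, then 1.0 mg BID x 11 weeks". Hydroxyzine follows the same pattern. Section 2.1 gives its maintenance dose as "25 mg in the morning and 50 mg at nighttime", and later in the same paragraph says "the evening dose is prescribed at 50 mg". No clock time is given.

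On side effects and tolerability, Section 13.1.2 states "Hypothesis testing will be conducted for only two outcomes". The second is "overall adherence (i.e., proportion of scheduled doses taken) assessed by daily medication diaries and returned capsules". Section 12.4 leaves missing values missing and analyses what was observed.

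**The concern.** A Yes/No question about a dose gives a clean answer only if the dose time has passed and the respondent knows which day is meant. Neither is secured here. The reply window is about 24 hours for a daily text, so a reply may come before the PM dose or on the following day. In the first case a truthful No is recorded for a dose taken soon afterwards. In the second the respondent may report the evening just past, which is right, or may read the words literally and answer for an evening that has not yet come. The morning item has a milder form of the same problem.

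A premature No is not treated like an unanswered text. An unanswered text stays missing under Section 12.4, whereas a premature No is an observed value and enters the analysis. Such errors follow the time of reply and not whether the drug was taken, and for early replies they run in one direction. At stake is the diary component of one of the two tolerability outcomes that are to be tested.

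**Working it through.** The plan states no adherence figure, benchmark or significance level, so there is no figure to reproduce. The check is a sensitivity calculation.

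**Inputs from Section 3.2**
- 3 days PM only, 4 days twice daily, then 11 weeks (77 days) twice daily: 3 + 4 + 77 = 84 days.
- PM occasions: 84. AM occasions: 4 + 77 = 81. Total: 165.
- PM share: 84/165 = 50.9%.

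**Assumptions**
- Exactly 84 treatment days, no dose adjustment and all texts answered.
- The same true adherence *a* for AM and PM doses, and AM answers correct.
- *f* = share of taken PM doses answered No. The documents do not give it, so it is varied over its range.

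**Formula**
Diary adherence = (81*a* + 84*a*(1 − *f*))/165 = *a*(1 − 0.509*f*).

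**Results**

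| *f* (assumed) | *a* = 100% | *a* = 90% |
|---|---|---|
| 0% | 100% | 90% |
| 5% | 97.5% | 87.7% |
| 10% | 94.9% | 85.4% |
| 25% | 87.3% | 78.5% |
| 50% | 74.5% | 67.1% |
| 100% | 49.1% | 44.2% |

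For a fully adherent participant, each 10% of taken PM doses answered No costs 0.10 × 84/165 = 5.1 percentage points.

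On days 1 to 3 the PM dose is the only one, so diary adherence there is *a*(1 − *f*): 90%, 75% and 50% for *f* of 10%, 25% and 50% when *a* = 100%.

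The calculation covers PM doses answered No in error. It does not model next-day replies that report the wrong day's dose, which could err either way.

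**The case against.** The strongest reply is that the mechanism depends on something the plan does not state. Other items in the same survey ask about cigarettes and stress over the current day, which suggests a reply late in the day. If the text is sent or answered after the PM dose, the answer is right, and a next-day reply may correctly report the evening before. This stands: misrecording is possible but does not follow from the wording alone.

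A reader might infer from the word 'evening' that the item misses a dose meant for bedtime. The documents do not support that, because Section 2.1 calls the same dose both an evening and a nighttime dose. The participant drug instructions (Appendices 17 and 18) are not in the text available for review and may fix the dose time.

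The safeguards are also real. Used and unused blister packs come back at Visits 3 to 7 (Section 8.7), and that count does not depend on when anyone replied. Text answers are reviewed with the participant at the same visits (Sections 8.4 and 8.5). Visit 3 falls six days after starting drug, so the PM-only days are looked at soon. These safeguards are incomplete, however. Later visits are up to four weeks apart, there is no rule for correcting a diary answer, a pack count does not date each dose, and Section 13.1.2 does not say how the two sources combine.

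Finally, the go/no-go rule uses nausea alone, so adherence drives no stopping or continuation decision.

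**Conclusion.** The point holds as a weakness of the instrument. With no send time, dose date or 'not yet' answer, and with replies accepted until the next message, a truthful reply can be stored as a missed dose. Diary adherence can therefore be biased, most plausibly downward, by up to about 5.1 points per 10% of taken PM doses answered No. That rests on 84 days, no dose adjustment and an assumed share of such replies. The actual size cannot be computed from the documents.

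A reader might go further and infer that night doses are recorded as missed and that the tested adherence result is wrong. The documents do not support this. The send time is unstated, the reply-timing shares are assumptions, and returned product is a named second source that reply timing does not affect. With no benchmark for the adherence test, no change in its result can be shown either. Nor can the combination be said to look worse than an alternative within the trial, which has a single group. The nausea rule is untouched.

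**What to change.** In Section 8.8.2 and Appendix 14, reword both dose items so that each names a completed, dated dose, for example 'yesterday morning' and 'last night' with the date shown. Changing only the evening item would leave the same problem for anyone who replies before the morning dose. Start these two items on the day after Visit 2, and leave the other survey items as they are, so that smoking, stress, sleep and nausea are still collected from the day of the visit.

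In Section 13.1.2, add a sentence on how diary answers and returned blister-pack counts are reconciled when they disagree. Letting the pack count decide is one option, but the need is for a stated rule.

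The cost is two reworded items and one sentence, slightly longer recall, and a first dose answer one day later. Dosing does not change.
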